15.6.2. Study Population

| Demographics and Baseline Characteristics | |
|---|---|
| Age | |
| | 
 • Age, in whole years, will be calculated with respect to the participant's Screening visit. For sub-study, age will be calculated with respect to the participant's first sub-study screening visit. • GSK standard IDSL algorithms will be used for calculating age where birth date will be imputed as follows: 
 ○ Any participant with a missing date and month will have this imputed as '30th June'. • Birth date will be presented in listings as 'YYYY'. • Completely missing dates of birth will remain as missing, with no imputation applied. Consequently, the age of the participant will not be calculated and will remain missing. |
| Body Mass Index (BMI) | |
| | 
 • Calculated as Weight (kg) / Height (m)² |
| Hepatitis Status | |
| | 
 • Hepatitis C status will be determined using antibody and/or hepatitis C virus (HCV) RNA assessments performed during screening or during the conduct of the study. • If both antibody and virus RNA assessments are available, then the latter will take precedence and positive/negative status will be based on whether HCV RNA is detectable (i.e., \geq limit of quantification) or not. • A participant will be considered positive for hepatitis B virus (HBV) if they have a positive surface antigen or detectable HBV DNA result. "HBV DNA DETECTED" in the lab comment takes precedence over HBV DNA test result for positive hepatitis B status, for example, if a participant has HBV test result below level of detection, however, the lab comment shows that HBV DNA detected, this participant will be considered positive for hepatitis B. If HBV DNA result is available, it will be used to qualify hepatitis B status as positive or negative (positive if \geq limit of quantification); otherwise Hepatitis B status will be determined using the surface antigen result. • Hepatitis status at entry will be based on the assessments prior to/on the start of the study treatment. |
| Framingham Risk Equation | |

| |
|--|
| Demographics and Baseline Characteristics |
|--|

- The predicted probability, \hat{p} , of having a cardiovascular disease (CVD) within the next 10-years according to the Framingham formula [D'Agostino, 2008] is

For females:

$$\hat{p}_F = 1 - S_0(t) \exp \left\{ \frac{2.32888 \times \log(\text{age}) + 1.20904 \times \log(\text{TC}) - 0.70833 \times \log(\text{HDL}) + 2.76157 \times \log(\text{SBP}_u) + 2.82263 \times \log(\text{SBP}_t) + 0.52873 \times I_s + 0.69154 \times I_d - 26.1931}{\exp \{ 3.06117 \times \log(\text{age}) + 1.12370 \times \log(\text{TC}) - 0.93263 \times \log(\text{HDL}) + 1.93303 \times \log(\text{SBP}_u) + 1.99881 \times \log(\text{SBP}_t) + 0.65451 \times I_s + 0.57367 \times I_d - 23.9802 \}} \right\}$$

For males:

$$\hat{p}_M = 1 - S_0(t) \exp \left\{ \frac{3.06117 \times \log(\text{age}) + 1.12370 \times \log(\text{TC}) - 0.93263 \times \log(\text{HDL}) + 1.93303 \times \log(\text{SBP}_u) + 1.99881 \times \log(\text{SBP}_t) + 0.65451 \times I_s + 0.57367 \times I_d - 23.9802}{\exp \{ 3.06117 \times \log(\text{age}) + 1.12370 \times \log(\text{TC}) - 0.93263 \times \log(\text{HDL}) + 1.93303 \times \log(\text{SBP}_u) + 1.99881 \times \log(\text{SBP}_t) + 0.65451 \times I_s + 0.57367 \times I_d - 23.9802 \}} \right\}$$

where

$$S_0(t) = \begin{cases} 0.95012, & \text{females} \\ 0.88936, & \text{males} \end{cases}$$

$$I_s = \begin{cases} 1, & \text{current smoker} \\ 0, & \text{otherwise} \end{cases}$$

$$I_d = \begin{cases} 1, & \text{diabetic} \\ 0, & \text{otherwise} \end{cases}$$

TC = total serum cholesterol (mg/dL),

HDL = serum HDL cholesterol (mg/dL),

SBPu = systolic blood pressure (mmHg) if participant is not treated for high blood pressure
(note that if a participant is treated for high blood pressure then $\log(\text{SBPu}) = 0$)

SBPt = systolic blood pressure (mmHg) if participant is treated for high blood pressure
(note that if a participant is not treated for high blood pressure then $\log(\text{SBPt}) = 0$)

- A participant will be considered as treated for high blood pressure if during screening it has specified that is suffering from hypertension.
- A participant is classified as diabetic if current or past is indicated in the medical conditions eCRF for Type 1 or Type 2 diabetes mellitus, or if baseline fasting glucose ≥ 7.00 mmol/L (126 mg/dL).
- Smoking status is collected in the eCRF at Day 1. A current smoker is defined as currently smoking/using tobacco or has smoked/used tobacco within the previous 6 months; a former smoker is defined as previously smoked/used tobacco products and has not smoked/used tobacco products within the previous 6 months.
- This calculation will not be performed for participants who have indicated current or past myocardial infarction conditions on the eCRF. These participants will not be included in summary statistics of risk, but they will be counted in the highest category of risk in the summary by category.

| |
|----------------------------------|
| Prior Exposure to CAB+RPV |
|----------------------------------|

- For participants transitioning from ATLAS study and having prior exposure to CAB+RPV in ATLAS study: Duration of Prior Exposure to CAB+RPV = Randomization Date – Prior Oral CAB Start Date in ATLAS Study + 1.

Demographics and Baseline Characteristics

- For participants transitioning from ATLAS study and not having prior exposure to CAB+RPV in ATLAS study, or for participants randomized from current SOC, Duration of Prior Exposure to CAB+RPV = 0.
- Duration of Prior Exposure to CAB+RPV will be categorized to 0 weeks, 1-24 weeks and >24 weeks.

Lipid-modifying Agents

- The following ATC codes correspond to lipid-modifying agents:
 - ATC Level 2: C10
 - ATC Level 3: C10A, C10B (if Level 2 is not available)
 - ATC Level 4: C10AA, C10AB, C10AC, C10AD, C10AX, C10BA, C10BX (if level 2, 3 are not available)
- Participants are considered to have used a lipid-modifying agent at baseline if they are taking the medication at the time of their baseline fasting lipid testing date.
- Participants are also considered to have used a lipid-modifying agent at baseline if they stopped their lipid modifying medication within 12 weeks prior to their baseline fasting lipid testing date.

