6. STUDY POPULATION ANALYSES

6.1. Overview of Planned Study Population Analyses

The study population analyses will be based on the Intent-to-Treat Exposed population, unless otherwise specified.

Study population analyses including analyses of subject's disposition, protocol deviations, demographic and baseline characteristics, prior and concomitant medications, and oral study treatment accountability will be based on GSK Core Data Standards.

[Table 1](#) provides an overview of the planned study population analyses, with details of the planned displays are presented in [Appendix 15: List of Data Displays](#).

Table 1 Overview of Planned Study Population Analyses

| Display Type | Data Displays Generated | |
|--|-------------------------|------------------|
| | Table | Listing |
| Randomization | | |
| Randomization ^[1] | | Y ^[2] |
| Subject Disposition | | |
| Study Populations ^[3] | Y | |
| Study Recruitment ^[3] | Y | |
| Reasons for Screening Failures ^[3] | Y | Y |
| Rescreened Subjects ^[3] | | Y |
| Age Ranges | Y | |
| Subject Disposition | Y ^{[4][5]} | |
| Reasons for Withdrawal | Y ^{[4][5]} | Y |
| IP Discontinuation | Y | Y |
| Important Protocol Deviations | Y | Y |
| Deviations leading to exclusion from PP | Y | Y |
| Inclusion and Exclusion Criteria Deviations | Y | Y |
| Demography and Baseline | | |
| Demographics Characteristics ^[6] | Y | Y |
| Race & Racial Combinations ^[7] | Y | Y |
| Hepatitis Status at Entry | Y | |
| Baseline CDC Classification of HIV infection (2014) | Y | |
| Baseline Cardiovascular Risk Assessments | Y | |
| Distribution of CD4+ Cell Counts at Screening and Baseline | Y | |
| Prior Exposure to CAB+RPV | Y | |
| HIV-1 Risk Factors | Y | |

| Display Type | Data Displays Generated | |
|---|-------------------------|---------|
| | Table | Listing |
| Medical Conditions, Concomitant Medications & Antiretroviral Therapy | | |
| Medical Conditions (Current/Past) ^[8] | Y | |
| Medical Conditions: Sub-conditions (Current/Past) ^[9, 10] | Y | |
| Concomitant Medications (non-ART) | Y ^[10] | |
| Prior ART Medications | Y | Y |
| Concomitant ART Medications during Maintenance Phase | | Y |
| ART Medications Received during LTFU Phase | | Y |
| Lipid Modifying Agents (Baseline and during Maintenance Phase) | Y | |
| Substance use at Entry | Y | |
| Medical History of Seizure | | Y |
| Other | | |
| Oral Study Treatment Accountability ^[11] | | Y |
| Transition to CAB+RPV LA Marketed Product | | Y |

NOTES:

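### The Framingham score counts every participant with recorded hypertension as treated for it, so recorded hypertensives not on treatment get an overstated baseline cardiovascular risk

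*SAP*

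**What the plan says.** The Framingham Risk Equation block of SAP Section 15.6.2 gives ten-year cardiovascular risk by sex. Systolic pressure enters through two terms, of which only one is active for any participant. The first is defined as "SBPu = systolic blood pressure (mmHg) if participant is not treated for high blood pressure" and the second as "SBPt = systolic blood pressure (mmHg) if participant is treated for high blood pressure"; the log of the inactive term is set to zero. The treatment indicator is then defined in these words: "A participant will be considered as treated for high blood pressure if during screening it has specified that is suffering from hypertension". No drug, ATC code or medication date is part of that rule, and I found nothing elsewhere in the SAP that qualifies it.

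The result is reported under "Baseline Cardiovascular Risk Assessments" in Table 1 of Section 6.1. Section 15.15.5.1 lists the corresponding table with Week 48 and Week 96 as its deliverables. An End-of-Study table number is printed in the same row, but End of Study is not in the deliverable column.

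**The concern.** The equation asks whether the participant is treated. The rule answers whether the participant has the condition. The two differ in both directions: a recorded hypertensive on no medication is scored as treated, and a participant taking blood-pressure medication without a hypertension entry is scored as untreated. The treated coefficient is the larger one for both sexes, so the first group is scored too high and the second too low.

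At stake is whether the table shows the score that the SAP cites. For misclassified participants it does not, by the equation's own definition of its terms.

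**Working it through.** The SAP states no risk figure, so there is nothing to reproduce. The check uses the coefficients printed in Section 15.6.2. The layout of the exponent is damaged in the extracted text, so I read the equation as risk = 1 − S0^exp(LP), with LP the linear predictor.

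**Inputs from the SAP**

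| | Untreated coefficient | Treated coefficient | Difference | S0 |
|---|---|---|---|---|
| Women | 2.76157 | 2.82263 | 0.06106 | 0.95012 |
| Men | 1.93303 | 1.99881 | 0.06578 | 0.88936 |

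**Step 1: multiplier for an untreated participant scored as treated.** Only the systolic term changes, so exp(LP) is multiplied by exp(difference × ln SBP).

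- Women at 140 mmHg: exp(0.06106 × 4.9416) = 1.352. Over 120 to 180 mmHg the range is 1.34 to 1.37.
- Men at 140 mmHg: exp(0.06578 × 4.9416) = 1.384. Over 120 to 180 mmHg the range is 1.37 to 1.41.

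ln SBP is positive, so the error is always upward for this group.

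**Step 2: effect on a given risk.** If p is the risk with the untreated coefficient, the reported risk is 1 − (1 − p)^multiplier. At 140 mmHg:

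| p | Men, reported | Women, reported |
|---|---|---|
| 10% | 1 − 0.90^1.384 = 13.6% | 1 − 0.90^1.352 = 13.3% |
| 15% | 1 − 0.85^1.384 = 20.1% | 1 − 0.85^1.352 = 19.7% |

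**Step 3: whole equation, with assumed covariates** (total cholesterol 190 mg/dL, HDL 48 mg/dL, non-smoker, non-diabetic, 140 mmHg; none of these values is in the SAP).

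| | Untreated coefficient | Under the SAP rule |
|---|---|---|
| Woman, 50 | 5.9% | 7.8% |
| Man, 50 | 9.4% | 12.8% |
| Man, 42 | 5.7% | 7.7% |

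For ages 35 to 60, 140 to 160 mmHg, smokers and non-smokers, and the same lipids, the relative overstatement is about 29% to 39%. The absolute overstatement is 0.9 to 10.2 percentage points, largest in older male smokers.

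**Step 4: how many participants.** The SAP gives no count. As a pure assumption, take 10% to 30% with recorded hypertension and 10% to 50% of those untreated. The misclassified share is then 0.10 × 0.10 = 1% to 0.30 × 0.50 = 15%, or about 10 to 153 of 1020. If each were overstated by 3.4 points, as for the 50-year-old man above, the mean over all participants would move by 0.01 × 3.4 = 0.03 to 0.15 × 3.4 = 0.51 points.

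**The case against.** Four arguments can be made for leaving the rule alone.

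**It is an explicit convention, and the form behind it is not shown.** The rule is written down in advance and points to something recorded at screening; the eCRF is not available to show what that item captures. This is fair as far as it goes. But as worded the rule refers to having hypertension, and stating a substitution does not make the score match the equation.

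**Nothing inferential rests on it.** This stands. The score is not among the subgroups or covariates of Section 5.4, nor in the efficacy, PK/PD or health-outcomes models. It is a pre-treatment summary and the same rule applies to both arms. A reader might infer that the error bears on the comparison of Q8W with Q4W; the SAP gives no basis for that.

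**The tables may already exist.** The listed deliverables are Week 48 and Week 96, and the table is absent from the Week 152 and sub-study lists. This SAP version is the amendment that adds the sub-study, so those tables have probably been produced. That does not remove the error, but it decides what the remedy can be.

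**Medication data would be another proxy.** This stands in part. A reader might infer that, because concomitant medications are collected, actual treatment is known. That goes too far. The SAP does not say that indication is used, drug class alone does not show treatment for high blood pressure, and Section 15.7.2.1 imputes partial dates, treats a wholly missing start date as before treatment and generally treats a wholly missing stop date as ongoing. Even so, medication records say something about treatment that a diagnosis alone does not.

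**Conclusion.** The point holds as a minor defect in a derived variable. The direction of the error is certain for recorded hypertensives not on treatment, and its size follows from the printed coefficients: about 1.38 times on exp(LP) in men and 1.35 in women at 140 mmHg, or roughly one third in relative risk terms. Recorded hypertensives who are on treatment are scored correctly.

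Two further inferences are not supported. The effect on the table as a whole is unknown, because the number of untreated hypertensives is not given and the range in Step 4 rests on assumed prevalences. Movement between risk categories cannot be shown either: Section 15.6.2 mentions a highest category, but the SAP states no cut-offs. The consequence is confined to the descriptive summary of baseline cardiovascular risk.

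**What to change.** In Section 15.6.2, set the treated indicator only when hypertension is recorded and an antihypertensive from a fixed ATC list is ongoing at baseline in the concomitant medication data. The schedules in Sections 15.2.1 and 15.2.2 collect concomitant medications at Screening and Day 1, and Section 15.6.2 already derives baseline lipid-modifying agent use from ATC codes and medication timing, so the method is in place. Use the revised flag in any further or repeated production of the table. For tables already issued, add a footnote that recorded hypertension was used as a proxy for treatment.

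The cost is one sentence in the SAP, one derived flag and an agreed ATC list, plus a rerun if corrected Week 48 or Week 96 tables are wanted. Requiring both conditions limits false positives from drugs given for other reasons, but drug class remains an imperfect marker of indication and partial dates still rely on imputation. Participants on antihypertensives without recorded hypertension stay classed as untreated, so their understated score is not repaired.

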15.6.3. Efficacy

| |
|--|
| Snapshot |
| 
 The Snapshot algorithm is intended to be primarily a virologic assessment of the endpoint, and as such follows a “virology first” hierarchy. ‘HIV-1 RNA < 50 c/mL’ or ‘HIV-1 RNA ≥ 50 c/mL’ within an analysis window (see Table 10 and Table 13) is typically determined by the last available HIV-1 RNA measurement in that window while the participant is On-treatment in the Maintenance Phase (as assigned based on Section 15.4). When no HIV-1 RNA data is available within a window, a participant cannot be assigned to the category of ‘HIV-1 RNA < 50 c/mL’. Depending on the reason for lack of data, the participant will be classified as ‘HIV-1 RNA < 50 c/mL’ or reported as ‘No Virologic Data at Week X’; in the latter case, the algorithm further classifies the nature of the missing data. Typically, a participant withdrawn (i) due to AE or, (ii) for another reason yet was suppressed at the time, will be counted as ‘No Virologic Data at Week X’. Should a participant withdraw for reasons other than AE and was not suppressed at the time, they will be categorized as ‘HIV-1 RNA ≥ 50 c/mL’. Full details of the algorithm, including the handling of special cases, are included in Section 15.9 |
| Plasma HIV-1 RNA |
| 
 For summaries and analyses which use HIV-1 RNA level as a continuous measure, the logarithm to base 10 of the value will be used. HIV-1 RNA results may be provided as censored values, such as <40 or >9,999,999 c/mL. For the purposes of summary statistics, such values will be replaced by the next value beyond the limit of detection, e.g., 39 or 10,000,000 c/mL, respectively, for the given examples. Data listings will show the censored values as provided. |
| Target Detected / Target Not Detected / Super Low Viral Load Testing |
| 
 When a measurement of plasma HIV-1 RNA is below the limit of quantification (i.e. 40 c/mL) and is qualitatively observable that will be denoted as a “Target Detected” measure, while HIV-1 RNA below the limit of quantification that is not qualitatively observable that will be denoted as “Target Not Detected”. Any measurements <40 c/mL characterised as “Target Not Detected” or “Target Detected” will be captured in the database. Super low viral load will also be tested by BioMONTR Labs for viral loads below the limit of quantification at some visits (e.g. Week 48). |
| Confirmed Virologic Failure (CVF) |
| 
 The definition of CVF is provided in the Protocol, Section 5.5.4 – Definition of Confirmed Virologic Failure. In case there are multiple plasma HIV-1 RNA results on the same day, the worst result (i.e. the largest value) will be used in determination of CVF. |
| Treatment (TRDF) and Efficacy Related (ERDF) Discontinuation = Failure |
| 
 The analysis of time to confirmed virologic failure (CVF) or discontinuation due to treatment related reasons (i.e., drug-related AE, intolerance of injections, protocol defined safety stopping criteria, or lack of efficacy) will censor participants who have not met CVF criteria and are ongoing in the study, or who have discontinued for reasons other than those related to treatment. This will be the Treatment Related Discontinuation = Failure (TRDF) data. |

- Participants who have not met CVF criteria and are ongoing in the study, or who have discontinued for reasons other than lack of efficacy, will be censored in the analysis of the Efficacy Related Discontinuation = Failure (ERDF) data.
- Proportion of Participants without virologic (ERDF) or tolerability (TRDF) failure will be estimated using the Kaplan-Meier nonparametric method based on the time to ERDF or TRDF. The estimated proportion at time point of interest will be presented by treatment group, along with estimated difference in proportions between treatment groups and its associated two-sided 95% CI. The estimate of the standard error used to derive confidence intervals will be based on Greenwood's formula [Kalbfleisch,1980].
- See [Appendix 10: Variables Defined for Time to Event Analysis](#) for additional details.

Summary for Participants per Viral Load Category by Visit

- Summary will be based on observed available data, with no imputation for missing values. The proportion of participants in each viral load category will be calculated using the denominator and numerator specified below:
 - Denominator: Number of participants with on-treatment viral load within the snapshot visit window.
 - Numerator: Number of participants with plasma HIV-1 RNA in the specified category based on the last on-treatment viral load assessment collected within the snapshot visit window.

HIV-1 Disease progression Stage

- Categories:
 - CDC Stage 1 at Baseline to CDC Stage II;
 - CDC Stage I at Baseline to CDC Stage III;
 - CDC Stage II at Baseline to CDC Stage III;
 - CDC Stage III at Baseline to new CDC Stage III event;
 - CDC Stage I, II, III at Baseline to Death.

Please refer to Protocol (Appendix 4: CDC Classification for HIV-1 Infection) for defining Stage.

- For the purpose of analysis, the CDC at Baseline and at post-baseline during Maintenance Phase will be derived as below:
 - At Baseline, the 'Baseline CDC stage' for each participant was assessed by investigator and recorded in the eCRF. However, for the analysis, Baseline CDC stage will be rederived based Baseline CD4+ values as well as whether any HIV-associated/AIDS-defining conditions present at baseline per the Criteria's thresholds (Appendix 4 in Protocol).
 - To analyse disease progression, the most advanced post-baseline CDC stage within the period of interest (e.g. Maintenance Phase) will be derived based on the occurrences of new AIDS-defining conditions (please refer to Appendix 4 in Protocol for the list of AIDS-defining Conditions) as well as the nadir value of post-baseline CD4+.
 - For example, if a participant with CDC 'Stage I' at Baseline had the lowest Maintenance Phase CD4+ =120 cell/mm³ without new AIDS-defining conditions, then HIV disease progression for this participant during the Maintenance Phase would be considered as 'CDC stage I at Baseline to CDC stage III'.
 - If a participant with CDC 'Stage II' at Baseline had the lowest Maintenance Phase CD4+ =220 cell/mm³ AND had at least one new AIDS-defining condition, then HIV

| |
|--|
| 
disease progression for this participant during the Maintenance Phase would be considered as 'CDC stage II at Baseline to CDC stage III'.
 |
| Delay in IP Injection |
| 
 For participants on the Q4W arm, IM dosing is expected to occur every 4 weeks from Week 4B onwards for those transitioning from SOC (i.e. those requiring oral lead-in) and from Day 1 onwards for those transitioning from CAB+RPV Q4W in ATLAS (i.e. those not requiring oral lead-in). The Delay in IP injection (days) will be calculated as: |
| $\text{Delay in IP Injection (days)} = \text{Injection date} - \text{date of preceding injection} - 28 \text{ days}$ |
| 
 For participants on the Q8W arm, IM dosing is expected to occur at Week 4B and then every 8 weeks from Week 8 onwards for those transitioning from SOC (i.e. those requiring oral lead-in) and every 8 weeks from Day 1 for those transitioning from CAB+RPV Q4W (i.e. those not requiring oral lead-in) in ATLAS. If participants receive reloading dose injection after oral bridging, the next IM dosing is expected to be 4 weeks from the reloading injection and then every 8 weeks onwards. 
 For participants transitioning from SOC on the Q8W arm, if the preceding injection occurs at Week 4B, the Delay in IP injection (days) will be calculated as: $\text{Delay in IP Injection (days)} = \text{Date of Week 8 injection} - \text{date of Week 4B injection} - 28 \text{ days}$ For participants receiving oral bridging medication and then returning to LA injections, if the preceding injection occurs at a reloading dose visit, the Delay in IP injection (days) will be calculated as: $\text{Delay in IP Injection (days)} = \text{Injection date} - \text{date of preceding injection} - 28 \text{ days}$ For participants transitioning from SOC on the Q8W arm, if the preceding injection occurs at a visit later than Week 4B or at non-reloading visit, the Delay in IP injection (days) will be calculated as: $\text{Delay in IP Injection (days)} = \text{Injection date} - \text{date of preceding injection} - 56 \text{ days}$ For participants transitioning from CAB+RPV Q4W in ATLAS on the Q8W arm, if the preceding injection occurs at non-reloading visit, the Delay in IP injection (days) will be calculated as: $\text{Delay in IP Injection (days)} = \text{Injection date} - \text{date of preceding injection} - 56 \text{ days}$ |
| 
 If the preceding study treatment is oral (e.g. CAB+RPV or SOC oral bridging), the Delay in IP injection (days) will be calculated as: 
 $\text{Delay in IP Injection (days)} = \text{Injection date} - \text{date of last oral dose on/prior to the injection date}$ Delay in IP injection will be grouped into: ≤ 1, 2-3, 4-7, > 7 days. The proportion of participants with HIV-1 RNA ≥ 50 c/mL at Week 48 (Snapshot) will be summarized by last delay in IP Injection. The last delay in IP injection will be the delay in IP injection at Week 48, or the delay in last IP injection prior to Week 48 if a participant did not receive Week 48 injection (i.e. missing visit or withdrawal). The similar analysis will be done for Week 96 and Week 152 timepoints where the proportion of participants with HIV-1 RNA ≥ 50 c/mL at Weeks 96 and 152 (Snapshot) and the delay in IP injection at Weeks 96 and 152 are considered respectively. |

